## Research Summary – Inhaled Pulmonary Vasodilators in Thoracic Transplantation & LVAD Surgery

hours after lung transplantation. The primary endpoint for the comparison of efficacy in LVAD patients will be incidence of moderate or severe RV failure according to Interagency Registry for Mechanically Assisted Circulatory Support (INTERMACS) scoring. The primary endpoint for the comparison of efficacy in the heart transplant subset will be the incidence rate of RVAD insertion. Secondary endpoints related to clinical outcomes for all populations will be duration of postoperative mechanical ventilation, ICU Length of Stay (LOS), hospital LOS, incidence of acute kidney injury, incidence of in-hospital mortality, as well as postoperative mortality at 30-days, 90-days, and 1-year after operation (Table 1).

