Based on recent *annual* operations, approximately 120 LVAD implantations, 60 heart transplantations, and 110 Lung transplantations were performed at Duke University Hospital during FY 2014 – 2015. This study has been individually powered to primary endpoints for each arm (Table 1) and the duration of study enrollment has been determined according to annual operations and sample-size calculations. We estimated sample size based on equivalence test of the incidence rates of a binary outcome (e.g. PGD grade 3 (PGD-3)) of two treatment groups as an illustration. Assuming the incidence rate of PGD-3 under iEPO treatment is 0.35 and acceptable margin of the equivalence is  $\pm 0.19$ , we will need 224 patients to have 80% power to detect an actual difference at 0.05 between two treatment group under this margin. This implies that the acceptable range of incidence rate for iNO treatment is from 0.21 to 0.59. Based on this estimate, we propose to enroll 200 lung transplant patients and 224 LVAD and heart transplant patients ( $n = 424$ ) over a period of 24 to 36 months; the exact time point for trial culmination between 24 and 36 months will be dependent on enrollment rate. There will be a 50% randomization rate for each inhaled agent such that 212 patients will receive iEPO and 212 patients will receive iNO.

**12. Data & Safety Monitoring:** The proposal is not introducing a new medication that has not been utilized by our group and safety has been established for this patient population through clinical practice and medication usage. Safety will, however, be determined by assessing reported, rare, adverse effects of iNO (systemic hypotension, methemoglobinemia, and rebound pulmonary hypertension after appropriate weaning) and iEPO (systemic hypotension, non-surgical bleeding related to thrombocytopenia, flushing, and rebound pulmonary hypertension after appropriate weaning) in order to accurately monitor adverse events (AE) during this study. The PI will review and sign off on AE's as they occur and perform a quarterly review and determine if AE's are related to the study or otherwise. AE's will be reported to the IRB per HRPP policies.

*Stopping Rule:* Subjects who meet the stopping criteria in section 4 continued to be enrolled and followed for primary outcome analysis. See section 4 for stopping criteria.

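### The heart-transplant RVAD endpoint is said to be individually powered, but the only calculation uses a PGD-3 rate of 0.35 and a ±0.19 margin, and neither supports an equivalence conclusion for RVAD insertion

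*Combined protocol and SAP*

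**What the plan says.** Section 11 of the combined protocol and SAP says of the trial: "This study has been individually powered to primary endpoints for each arm (Table 1"). The Table 1 footnote likewise says the sample size is powered for the primary outcomes. Only one calculation follows: "We estimated sample size based on equivalence test of the incidence rates of a binary outcome (e.g. PGD grade 3 (PGD-3)) of two treatment groups". Its inputs are "Assuming the incidence rate of PGD-3 under iEPO treatment is 0.35", a margin of ±0.19, and the statement that "we will need 224 patients to have 80% power to detect an actual difference at 0.05 between two treatment group under this margin". The section calls this an illustration, but both enrolment targets rest on it: "Based on this estimate, we propose to enroll 200 lung transplant patients and 224 LVAD and heart transplant patients".

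Section 4 (Measured Outcomes) says: "The primary endpoint for the comparison of efficacy in the heart transplant subset will be the incidence rate of RVAD insertion". Table 1 agrees. No expected RVAD rate, no margin for RVAD insertion, no number of heart-transplant patients within the 224, and no reason for choosing 19 points appear anywhere.

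The analysis text of Section 11 does not use the margin. It treats the two drugs as equivalent when the treatment effect is not significant.

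**The concern.** An absolute margin set beside a 35% event does not carry over to an event of unknown and possibly much lower frequency. At 0.35, ±0.19 allows up to 0.54, about 1.5 times the reference. At a low rate the same 19 points allows a several-fold increase. The 224 also covers two populations with different primary endpoints, so the RVAD comparison uses only the heart-transplant part.

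The stated purpose is to support iEPO as an acceptable alternative to iNO, with cost as a main motive. A conclusion of similar RVAD use that the data could not support would bear directly on that decision.

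**Working it through.** **Inputs from Section 11.** PGD-3 rate 0.35; margin 0.19; actual difference 0.05; power 80%; N = 224, so 112 per arm; annual volumes of 120 LVAD implantations and 60 heart transplants.

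**Assumptions, not in the documents.** RVAD reference rates of 5%, 10% and 15%. A heart-transplant share following annual volume: 224 × 60/180 = 74.7, or about 37 per arm. Alpha is not clearly stated.

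**1. The plan's own figure.** For two one-sided tests by normal approximation, power = Φ((0.19 − δ)/SE − z) + Φ((0.19 + δ)/SE − z) − 1, with SE = √[(0.35 × 0.65 + 0.40 × 0.60)/n].
- At n = 112, SE = √(0.4675/112) = 0.0646. With δ = 0.05 the two ratios are 0.14/0.0646 = 2.167 and 0.24/0.0646 = 3.715.
- Alpha 0.10 per side (z = 1.282): power 0.80; required N = 222.
- Alpha 0.05 per side (z = 1.645): power 0.68; required N = 300.
- Alpha 0.05 per side, both rates 0.40, no true difference: N = 228. The printed range of 0.21 to 0.59 is centred on 0.40.

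So 224 can be reproduced approximately, but only from rates of 0.35 to 0.40. No RVAD input enters it.

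**2. What the margin permits at other rates.** Upper limit = p + 0.19; ratio = (p + 0.19)/p.

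| Reference rate | Upper limit | Ratio |
|---|---|---|
| 0.05 | 0.24 | 4.8 |
| 0.10 | 0.29 | 2.9 |
| 0.15 | 0.34 | 2.3 |
| 0.19 | 0.38 | 2.0 |
| 0.35 | 0.54 | 1.5 |

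These are statements about true rates, not about passing a test.

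**3. How often a margin test would pass.** Suppose equivalence is declared when the 90% Newcombe interval for the risk difference lies inside ±0.19. With p₁, p₂ the observed rates, d = p₂ − p₁ and l, u the Wilson limits, the interval runs from d − √[(p₂ − l₂)² + (u₁ − p₁)²] to d + √[(u₂ − p₂)² + (p₁ − l₁)²]. Binomial probabilities are summed over every pair of counts, 37 per arm:

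| Reference rate | Identical drugs | True 1.5-fold | True doubling |
|---|---|---|---|
| 5% | 88% | 78% | 63% |
| 10% | 67% | 49% | 27% |
| 15% | 49% | 28% | 9% |

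For comparison, PGD-3 at 0.35 against 0.525 (1.5-fold) with 100 per arm passes 7.6%. A larger sample does not cure the low-rate problem: with 112 per arm, a doubling from 5% passes 98%.

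**4. The rule as written.** With 37 per arm and a two-sided 5% Fisher test, a true doubling is non-significant 97% of the time at 5%, 86% at 10% and 75% at 15%.

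**The case against.** The strongest objection is that the plan contains no margin test. Its rule is the absence of a significant difference, so the pass rates in step 3 describe a procedure the plan does not prescribe. That is correct, and it means the margin is not what would make an RVAD result count as equivalent today. It does not rescue the endpoint. Step 4 shows the written rule would miss a doubling more often than not at all three rates, and replacing it with a margin test would leave only ±0.19 to test against.

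Second, the RVAD rate and the 37-per-arm split are assumed, and the answer changes across the range. That stands, and the conclusion is conditional for that reason. The absence of any RVAD rate, margin or sample size is not conditional.

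Third, judging harm by a ratio is a choice: 1.5-fold at 5% is 2.5 percentage points. That is fair. But the plan offers no reason for 19 points on the absolute scale either, for RVAD insertion or for PGD-3.

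Fourth, the calculation is labelled an illustration. No other is given, and the pooled enrolment target is exactly its output.

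**Conclusion.** The claim that heart-transplant RVAD insertion is individually powered is unsupported. This follows from the text alone.

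What the margin does depends on a rate the documents do not give. At about 10% or lower, ±0.19 is uninformative: with 37 per arm a 1.5-fold rate passes 78% of the time at 5% and 49% at 10%, and a doubling 63% and 27%. At 15% a doubling passes only 9%, but identical drugs pass only 49%, so the subset cannot support an equivalence conclusion there either. These figures rest on the assumed split and the supplied interval rule.

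A reader might infer three stronger things, none of which holds:
- That at every rate below 0.19 a doubling would usually be declared equivalent. It lies within the margin as a true difference, but passes a test only 9% of the time at 15% and 4% at 18%.
- That the lower limit can never be breached at low rates. The true difference cannot go below it, but the interval can: with identical drugs this happens 6%, 17% and 26% of the time at 5%, 10% and 15%.
- That a low rate simply makes passing too easy. At 10% and 15% identical drugs pass less often than the planned 80%.

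**What to change.** In the sample-size text of Section 11 and the Table 1 footnote, state that the calculation and the ±0.19 margin apply to PGD-3 only, and remove the claim that heart-transplant RVAD insertion is individually powered.

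In the analysis text of Section 11, state that no equivalence conclusion will be drawn for RVAD insertion, whether from a non-significant test or from ±0.19. Report RVAD counts by arm, with the risk difference and risk ratio and exact or score 95% confidence intervals, labelled as estimation.

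This changes wording only and adds no patients or procedures. The cost is that the sponsor gives up a formal equivalence statement for RVAD insertion. Confining the margin to PGD-3 also leaves LVAD right ventricular failure without a stated margin, so the sponsor should say separately what inference is intended there.

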**Table 1. Study Summary**

§Sample Size	N = 424 (50/50 by randomization strata)
Population	1. Lung transplantation (N = 200) 2. Heart Transplantation / LVAD implantation (N = 224)
Rationale	
 
• Comparison of iNO and iEpo impact on outcomes – evaluate for equivalency
 
• PVD therapy indications:               
 
1. Lung Transplant: Improvement of ventilator and perfusion matching after lung allograft implantation by vasodilation of ventilated pulmonary capillaries
 
2. Heart Transplant/LVAD Implantation: Improvement of RV contractility after cardiac allograft implantation or LVAD implantation by PVR reduction
 
 
 

Study Design	Prospective, Randomized, Double-Blinded
Primary Outcomes	1. Lung Transplant: Severe PGD (grade 3) 2a. Heart Transplant: RVAD insertion b. LVAD: INTERMACS Moderate or Severe RVF
Secondary Outcomes	All populations: 
 
• ICU LOS (days)
 
• Hospital LOS (days)
 
• Mechanical ventilator duration (hours)
 
• Postoperative AKI
 
• In-hospital mortality
 
• Mortality 30-day, 90-day, 1-year
 

Study length*	24-36 months

§Sample size powered for primary outcomes

\*Study length is determined through sample size divided by annual operations at Duke University Hospital; AKI = Acute kidney injury; iEpo = inhaled epoprostenol; iNO = Inhaled nitric oxide; ICU = Intensive care unit; LOS = Length of stay; LVAD = Left ventricular assist device; PGD = Primary graft dysfunction; PVD = Pulmonary vasodilators; PVR = Pulmonary vascular resistance; RVF = Right ventricular failure

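### The one sample-size calculation shown needs 224 patients for the lung endpoint but 200 lung patients are planned; its equivalence limits do not match its margin, and the powering claim for LVAD and heart transplant has no stated inputs

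*Combined protocol and SAP*

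**What the plan says.** Section 11 (Data Analysis & Statistical Considerations) claims "This study has been individually powered to primary endpoints for each arm (Table 1"), and the footnote to Table 1 repeats it: "Sample size powered for primary outcomes".

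One calculation follows. It is described as an equivalence test "of a binary outcome (e.g. PGD grade 3 (PGD-3)) of two treatment groups as an illustration". The inputs are a PGD-3 rate of 0.35 under iEPO and a margin of ± 0.19, and the result is that "we will need 224 patients to have 80% power to detect an actual difference at 0.05 between two treatment group under this margin". The next sentence reads "This implies that the acceptable range of incidence rate for iNO treatment is from 0.21 to 0.59", and the one after it "Based on this estimate, we propose to enroll 200 lung transplant patients and 224 LVAD and heart transplant patients".

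Table 1 and Section 4 (Measured Outcomes) make PGD-3 the primary endpoint for lung transplant only. For LVAD patients it is "INTERMACS Moderate or Severe RVF", and for heart transplant patients it is RVAD insertion. Table 1 gives these last two groups one combined total of 224.

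**The concern.** Three things do not fit together.

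- **Lung sample size.** The calculation for the lung endpoint asks for 224 patients and the lung cohort gets 200. The figure of 224 goes to a cohort with different endpoints. No reason is given.
- **Equivalence limits.** The margin and the range in adjacent sentences give different limits: an upper limit of 0.54 or 0.59, and a lower limit of 0.16 or 0.21. An iNO rate of 0.57, for example, lies inside one set and outside the other.
- **LVAD and heart transplant.** The claim of separate powering covers endpoints for which no rate, margin, calculation or patient number is given.

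Showing equivalence is the purpose of the trial (Section 2; Table 1, Rationale). Limits left open until outcomes are known could be chosen to suit the result. A reader also needs to know the chance that the lung comparison succeeds, and what the other two comparisons can show.

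**Working it through.** **Inputs from Section 11.** iEPO rate 0.35; margin 0.19; true difference 0.05, hence iNO 0.40; power 80%; required total 224 (112 per arm); planned lung total 200 (100 per arm at 1:1). **Assumption:** two one-sided tests at 0.05 per side, because the plan does not state alpha.

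**Limits.**
- 0.35 ± 0.19 = 0.16 to 0.54
- 0.40 ± 0.19 = 0.21 to 0.59, the printed range
- Relative to iEPO at 0.35 the printed range is 0.21 - 0.35 = -0.14 and 0.59 - 0.35 = +0.24

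**Reproducing 224.** If the limits are centred on the true difference, each lies 0.19 from it, and for 80% power

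n per arm = V × (1.645 + 1.282)² / 0.19² = V × 237.2

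- Pooled variance: V = 2 × 0.375 × 0.625 = 0.46875, so n = 111.2, rounded up to 112 per arm, **224 in total**
- Unpooled variance: V = 0.35 × 0.65 + 0.40 × 0.60 = 0.4675, so n = 110.9, rounded up to 111 per arm, 222 in total

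This accounts for every printed figure: 0.35, 0.05, 0.19, 0.21 to 0.59, 224 and 80%. The 0.05 difference costs no power here, because the limits have moved with it.

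**Power.** With d the true difference, L and U the limits, and SE = √(V/n),

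power = Φ((U - d)/SE - 1.645) - Φ((L - d)/SE + 1.645)

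*Limits -0.14/+0.24, d = 0.05, 100 per arm:* SE = √(0.4675/100) = 0.0684; Φ(1.134) - Φ(-1.134) = 0.872 - 0.128 = 0.743.

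*Limits ± 0.19, d = 0.05, 100 per arm:* Φ(0.403) - Φ(-1.865) = 0.656 - 0.031 = 0.625. At 150 per arm SE = 0.0558 and Φ(0.863) - Φ(-2.654) = 0.806 - 0.004 = 0.802, so 300 patients are needed.

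*Limits ± 0.19, d = 0, both rates 0.35, 100 per arm:* V = 0.455, SE = 0.0675; Φ(1.172) - Φ(-1.172) = 0.759.

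| iEPO / iNO | iNO limits | Total for 80% | Power at 224 | Power at 200 |
|---|---|---|---|---|
| 0.35 / 0.40 | 0.21 to 0.59 | 222 to 224 | 80.5% | 74% |
| 0.35 / 0.40 | 0.16 to 0.54 | 300 | 68% | 62.5% |
| 0.35 / 0.35 | 0.16 to 0.54 | 216 | 82% | 76% |

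Exact binomial enumeration of the same Wald tests agrees: 80.5% and 73.9% in the first row, 68.7% and 62.0% in the second, 82.1% and 76.0% in the third.

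**Sensitivity to alpha.** At 0.025 per side the first row needs 274, so that level cannot lie behind 224. At 0.10 per side the second row needs 222, but it does not produce the printed range; its power at 200 is 78%, still below 80%.

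**LVAD and heart transplant.** No calculation is possible. The documents give neither event rates nor margins for these endpoints, and no split of the 224.

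**The case against.** The strongest reply is that the calculation is internally coherent and offered only as an illustration. Much of this stands. One reading gives exactly 224 and the printed range together, so the range is not a random slip. The plan words 0.05 as a true difference, so it is alpha that is missing. The 80% is printed for 224 patients and never for 200; for lung it is implied, by basing enrolment on the estimate and by claiming that each primary endpoint is powered. The shortfall is 24 of 224 (11%), and the loss under the coherent reading is about 6 percentage points.

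The illustration argument does not remove the point. If the PGD-3 calculation is not the lung calculation, then lung has none, and the powering claim is unsupported for all three endpoints.

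Three stronger readings are tempting, and the documents do not support them:

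- *That the LVAD and heart cohorts are underpowered.* Without rates, margins and a split, the claim can be shown neither true nor false.
- *That the range is a misprint, cured by changing it to 0.16 to 0.54.* That edit alone would break the agreement with 224: with the 0.05 difference kept, the requirement becomes 300.
- *That the conflicting limits would by themselves alter the trial's conclusion.* The analysis rule in Section 11 infers equivalence from a non-significant treatment effect and uses no margin. The powers above describe the equivalence test named in the sample-size paragraph, not that rule.

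**Conclusion.** The point holds in this form. The plan's own calculation for the lung endpoint requires 224 patients and the lung cohort is 200, so the implied 80% power is not delivered. Power at 200 is about 74% with the printed range, about 62% with ± 0.19 around 0.35 and a true difference of 0.05, and about 76% with those limits and no true difference. All three assume two one-sided tests at 0.05 per side.

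The margin and the range give different limits. They are linked through the 224, which depends on limits of -0.14 and +0.24 relative to iEPO, not the symmetric ± 0.19 that the text states. This part matters more than the 24 patients, because settling it decides whether the requirement is about 224 or 300.

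For LVAD RV failure and heart-transplant RVAD insertion the finding is an unsupported claim, not an arithmetical error.

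**What to change.** No added patients are needed. In Section 11, and in the Table 1 footnote where it applies:

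1. State alpha per side and the assumed true iNO rate.
2. Before unblinded outcome data are seen, state one set of equivalence limits relative to the iEPO rate. Recompute the required number and the power under those limits; do not edit the printed range alone.
3. Restate lung power for the planned cohort, for example: *With 200 lung patients (100 per arm), two one-sided tests at [alpha] per side, iEPO rate [rate], true iNO rate [rate] and iNO limits [lower to upper], power is about [x]%.* At 0.05 per side, x is about 74 for 0.35, 0.40 and 0.21 to 0.59; about 62 for 0.35, 0.40 and 0.16 to 0.54; and about 76 for 0.35, 0.35 and 0.16 to 0.54.
4. For LVAD and heart transplant, give the event rates, margins, expected numbers and calculation for each endpoint, or withdraw the powering claim and the Table 1 footnote for those endpoints.

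The cost is protocol wording and a short recalculation, with no extra visits or data. The stated lung power becomes less favourable, and the sponsor must either produce the LVAD and heart inputs or give up the claim for them.

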**11. Data Analysis & Statistical Considerations:** Summary statistics will be computed for demographic, clinical, and outcome variables in the form of frequencies (percentage) for categorical variables and mean (standard deviation) for continuous variables for each arm. Univariate analysis will be performed to compare the difference of each variable between treatment groups by chi-square or Fisher exact tests for categorical variables, and t-tests or Wilcoxon Rank-Sum tests for continuous variables depending on data normality. The univariate results for the outcome variables will provide information on iNO treatment effect in comparison to iEPO without taking into account other potential confounding factors. All non-outcome variables meeting  $p < 0.15$  association with treatment group will be considered for variable selection to build a multivariable regression model. For each outcome of interest, we will start with a regression model (logistic regression for binary outcomes or generalized linear model for continuous outcomes) with all variables selected from univariate analysis described above. Based on stepwise variable selection, we will determine the final set of covariates to be included in the final multivariable model to test the treatment group effect. Based on the analysis results, we will be able to understand if iNO is equivalent to iEPO (no significant difference) or significantly better or worse than iEPO (significant treatment effect) to address the efficacy of iNO for Aim 1. Several of secondary measures will be obtained over time. We will apply generalized mixed model to take into account the repeated measures over time to test for treatment effect. In the case of patients have switched to the other arm due to clinical decision, we will conduct the primary analysis based on the intent to treat (ITT) without reclassifying treatment assignment. In addition, protocol analysis, where only patients follow the protocol assignment are included will also be conducted to verify ITT results. For Aim 2 to compare cost capture analysis, the comparison of cost measures between two groups will be tested by two sample t-test.

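### The printed acceptable iNO range (0.21 to 0.59) contradicts the stated 0.35 ± 0.19, which gives 0.16 to 0.54, and the power for 200 lung patients is unsupported

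*Combined protocol and SAP*

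**What the plan says.** The sample-size text in Section 11 (Data Analysis & Statistical Considerations) is built on an equivalence test of PGD-3 rates, offered as an illustration:

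- **Inputs:** "Assuming the incidence rate of PGD-3 under iEPO treatment is 0.35 and acceptable margin of the equivalence is" ±0.19.
- **Claim:** "we will need 224 patients to have 80% power to detect an actual difference at 0.05 between two treatment group under this margin".
- **Implied limits:** "This implies that the acceptable range of incidence rate for iNO treatment is from 0.21 to 0.59".
- **Enrolment, set from this estimate:** "we propose to enroll 200 lung transplant patients and 224 LVAD and heart transplant patients", allocated 1:1.

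The same section says "This study has been individually powered to primary endpoints for each arm", and the Table 1 footnote says "Sample size powered for primary outcomes". PGD-3 is the primary endpoint of the lung group only, so the calculation applies to the group given 200 patients, not the one given 224.

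The analysis part of Section 11 uses a stepwise-selected "final multivariable model to test the treatment group effect" and then concludes: "we will be able to understand if iNO is equivalent to iEPO (no significant difference"), with a significant effect read as better or worse. It gives no significance level and does not mention the margin.

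**The concern.** The reference rate and margin do not produce the range said to follow from them, so the plan holds two incompatible sets of equivalence limits for one primary endpoint. Relative to an iEPO rate of 0.35, the printed range allows iNO to be 0.24 worse but only 0.14 better, whereas the stated margin is symmetric.

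The contradiction also puts the sample size in doubt. If 224 was derived from limits other than ±0.19, the 80% claim does not belong to the stated margin. The lung group then receives 24 fewer patients than the number said to be needed, with no power stated for it.

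The trial exists to judge whether the two drugs are equivalent. The limits, the power to meet them and the rule for declaring them met should therefore agree, and at present they do not.

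**Working it through.** **Inputs from Section 11.** iEPO rate 0.35; margin ±0.19; difference 0.05, direction not given (iNO 0.40 or 0.30); N = 224 for 80% power; 1:1 allocation, so 112 per arm at 224 and 100 per arm at 200. **Not stated:** alpha for the equivalence test (0.05 per one-sided test assumed; 0.025 and 0.10 also shown) and dropout (none assumed).

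**1. The range.** 0.35 − 0.19 = 0.16 and 0.35 + 0.19 = 0.54. The printed limits equal 0.40 − 0.19 = 0.21 and 0.40 + 0.19 = 0.59. Around 0.35 they are 0.21 − 0.35 = −0.14 and 0.59 − 0.35 = +0.24. No assumption is needed.

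**2. The stated 224.** Two one-sided tests (TOST), normal approximation, unpooled variance, with d the true difference and m the margin:

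SE = √{[p₁(1 − p₁) + p₂(1 − p₂)]/n per arm}

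Power = Φ((m − d)/SE − z) + Φ((m + d)/SE − z) − 1, with z = 1.645 at one-sided alpha 0.05.

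- iNO 0.40, 112 per arm: SE = √(0.4675/112) = 0.0646. Power = Φ(0.14/0.0646 − 1.645) + Φ(0.24/0.0646 − 1.645) − 1 = 0.699 + 0.981 − 1 = 0.680.
- iNO 0.30, 112 per arm: SE = √(0.4375/112) = 0.0625. Power = 0.724 + 0.986 − 1 = 0.710.

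So 224 does not give 80% on these inputs at alpha 0.05. All scenarios with iEPO 0.35 and limits ±0.19:

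| One-sided alpha | True iNO rate | Power at 224 | Power at 200 | N for 80% |
|---|---|---|---|---|
| 0.025 | 0.40 | 54% | 47% | 378 |
| 0.025 | 0.30 | 58% | 51% | 354 |
| 0.025 | 0.35 | 69% | 61% | 266 |
| 0.05 | 0.40 | 68% | 63% | 300 |
| 0.05 | 0.30 | 71% | 66% | 280 |
| 0.05 | 0.35 | 82% | 76% | 216 |
| 0.10 | 0.40 | 80% | 77% | 222 |
| 0.10 | 0.30 | 83% | 79% | 208 |
| 0.10 | 0.35 | 91% | 88% | 166 |

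Exact binomial enumeration of the same test at alpha 0.05 agrees: 68.7% and 71.1% at 224, 62.0% and 66.4% at 200 (iNO 0.40 and 0.30).

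**3. Where 224 could come from.** Several readings come close, so its origin is not established:

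- Shifted limits −0.14/+0.24, alpha 0.05, iNO 0.40: N = 222 (224 with pooled variance). With iNO 0.30, power at 224 under these limits is 42%.
- ±0.19, alpha 0.10, iNO 0.40: N = 222.
- Both arms 0.35, no difference, alpha 0.05: N = 216.
- Both arms 0.40, no difference, alpha 0.05: N = 228, power 79% at 224 and 73% at 200. This reading also yields 0.21 to 0.59.

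**4. Effect of the limits and the rule.** Exact probability of declaring equivalence, 100 per arm, iEPO 0.35:

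| True iNO rate | 90% CI within ±0.19 | 90% CI within −0.14/+0.24 | Unadjusted chi-square, p ≥ 0.05 two-sided |
|---|---|---|---|
| 0.54 | 4.8% | 17.2% | 21.2% |
| 0.16 | 5.1% | 0.7% | 12.2% |
| 0.35 | 76.0% | 63.8% | 95.0% |

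For example, 35/100 on iEPO against 48/100 on iNO gives p = 0.06 (chi-square, no continuity correction). The difference is 0.13 with SE 0.069, so the 90% CI runs from +0.016 to +0.244. An unadjusted non-significance rule would call that equivalent although the interval passes +0.19.

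**The case against.** Five points can be made for the plan.

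- **The power shortfall is conditional.** Alpha is unstated, and the 0.05 in the power sentence could be meant as the significance level rather than a true difference. With no true difference and one-sided alpha 0.05, 224 gives 82% (both arms 0.35) or 79% (both arms 0.40). The second case also reproduces the printed range, so 0.35 may be the stray figure. This stands: a shortfall at 224 is not proven. On these same readings, however, 200 lung patients give only 76% or 73%.
- **The comparison of limits depends on which set is right.** At a true iNO rate of 0.16 the shifted limits are stricter (0.7% against 5.1%), and under the printed range 0.54 is an acceptable rate. True, but this shows why the limits must be settled rather than that the discrepancy is harmless.
- **The misprint changes no planned conclusion,** because the analysis text applies neither set of limits. Also true, and it exposes a separate defect: an equivalence design without an equivalence decision rule.
- **The 21% is unadjusted,** whereas the final test is covariate-adjusted with no stated significance level. It is therefore illustrative only.
- **The calculation is called an illustration,** and no power is claimed for 200. But enrolment is set from it, and the plan describes itself as powered for its primary outcomes.

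**Conclusion.** The concern holds and must be fixed. The range contradiction is certain: 0.35 ± 0.19 is 0.16 to 0.54, and both printed limits are off by 0.05. If 0.40 was the intended reference rate, the stated 0.35 is wrong instead, and the text still needs correcting.

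The 80% claim for 224 cannot be confirmed. It fails at one-sided alpha 0.05 or below with a true difference of 0.05, and is met at alpha 0.10 with that difference, or at alpha 0.05 with none. For the 200 lung patients, power is below 80% at every alpha tried when the difference is 0.05. With equal rates it passes 80% only at alpha 0.10. These figures assume TOST, 1:1 allocation and no dropout.

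Inferring equivalence from non-significance is a separate error, and correcting the range alone would leave it in place.

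**What to change.** 1. Reconcile the reference rate and the range: print 0.16 to 0.54 if 0.35 stands, or correct the reference rate if 0.40 was intended.
2. State the alpha of the equivalence test, and the size and direction of the assumed true difference.
3. Restate the power that 224 and 200 patients give under ±0.19 on those assumptions, without adding patients. For 200 patients at a reference of 0.35, over one-sided alpha 0.025 to 0.10, the figure is 47% to 79% with a 0.05 difference or 61% to 88% with none. At a reference of 0.40 it is 45% to 77% or 57% to 86%. Align the Table 1 footnote and the powering claim in Section 11 with the result.
4. As a separate correction, replace the non-significance rule in Section 11: conclude equivalence only if the confidence interval for the PGD-3 risk difference lies wholly within ±0.19 (a 90% interval if one-sided alpha is 0.05). If the logistic model remains the primary analysis, state how the risk difference is obtained from it.

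The cost is text only: no new data and no added patients. The downside is a less favourable stated power and a stricter rule. With a true rate of 0.35 in both arms of 100, equivalence is declared 76% of the time, against 95% under an unadjusted non-significance rule.

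### The 224 heart/LVAD patients are sized for one comparison but carry two different primary endpoints, so the stated 80% power is not supported for either

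*Combined protocol and SAP*

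**What the plan says.** The Measured Outcomes part of section 4 assigns endpoints by operation. For LVAD: "The primary endpoint for the comparison of efficacy in LVAD patients will be incidence of moderate or severe RV failure", on the INTERMACS scale. For heart transplant: "The primary endpoint for the comparison of efficacy in the heart transplant subset will be the incidence rate of RVAD insertion". Table 1 lists them as items 2a and 2b.

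The sample is not split the same way. Table 1 has one line, "Heart Transplantation / LVAD implantation (N = 224", and the Subject Groups paragraph and section 11 repeat the joint number without a quota for either operation. Section 11 puts it this way: "we propose to enroll 200 lung transplant patients and 224 LVAD and heart transplant patients".

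On power, section 11 says: "This study has been individually powered to primary endpoints for each arm (Table 1". A footnote to Table 1 also says that the sample is powered for the primary outcomes. The one calculation shown is described as illustrative and rests on a lung outcome: "Assuming the incidence rate of PGD-3 under iEPO treatment is 0.35", with an equivalence margin of ±0.19, giving 224 patients for 80% power.

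The analysis text in section 11 fits a regression model for each outcome and reads a non-significant treatment effect as equivalence. It does not say whether the LVAD and heart-transplant endpoints are analysed separately or merged.

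**The concern.** A sample size belongs to a comparison on one outcome. Here no single outcome is defined for all 224 patients. An LVAD recipient with moderate RV failure and no RVAD is an event; a heart recipient in the same state is not. If the endpoints are analysed one at a time, each has only part of the 224. If they are merged, the result mixes two different events.

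The trial is meant to support an equivalence conclusion that could change which drug is used. A reader who trusts the power statement will take a heart/LVAD result as having 80% power for the endpoint of interest, when the plan shows this for neither endpoint. Leaving the choice between separate and merged analysis open also allows it to be made after the data are seen.

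**Working it through.** **Inputs from the documents (section 11).** Rate 0.35 (lung), margin m = 0.19, total 224 at 1:1 (112 per drug), 80% power, and annual volumes of 120 LVAD and 60 heart transplants.

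**Assumptions.** One-sided alpha of 0.05 for each of two one-sided tests (sidedness is not stated). RVAD rates of 0.05 to 0.15 (none is given). Recruitment in proportion to annual volume.

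**Formula.** With n per drug, rates p1 and p2, and d = p2 − p1:

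SE = √[(p1(1−p1) + p2(1−p2))/n]

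power = Φ((m−d)/SE − 1.645) + Φ((m+d)/SE − 1.645) − 1

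**1. The plan's 224.** At 0.35 with d = 0 and n = 112: SE = √(0.455/112) = 0.0637; 0.19/0.0637 = 2.98; power = 2Φ(1.336) − 1 = 82%. The plan also says that "the acceptable range of incidence rate for iNO treatment is from 0.21 to 0.59", which is centred on 0.40; at 0.40 the power is 79%. So 224 is the size of one two-group comparison. Reading the plan's 0.05 as a true difference (0.35 v 0.40) does not reproduce it: power would be 68%.

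**2. Split of the 224.** 224 × 120/180 = 149 LVAD (74.7 per drug); 224 × 60/180 = 75 heart (37.3 per drug).

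**3. LVAD alone.**

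| RV-failure rates | SE | Power |
|---|---|---|
| 0.35 v 0.35 | 0.0781 | 57% |
| 0.35 v 0.40 | 0.0791 | 47% |
| 0.35 v 0.30 | 0.0765 | 51% |
| 0.20 v 0.20 | 0.0655 | 79% |

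For LVAD shares of 60% to 75%, the first row becomes 49% to 65%.

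**4. Heart transplant alone, no true difference.**

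| RVAD rate (assumed) | SE | Power |
|---|---|---|
| 0.05 | 0.0504 | 97% |
| 0.10 | 0.0694 | 72% |
| 0.15 | 0.0826 | 49% |

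At 0.05 the margin is nearly four times the event rate (0.19/0.05 = 3.8), and about two events per drug are expected (37.3 × 0.05 = 1.9). The high power reflects the wide margin.

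**5. If the endpoints were pooled.** Assume LVAD rates of 0.35 v 0.54 (a true difference equal to the margin) and no difference in heart patients. The pooled difference is (2/3) × 0.19 = 0.127. Simulated chance of calling the drugs equivalent (200,000 trials, 112 per drug; LVAD alone at 75 per drug):

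| Decision rule | LVAD alone | Pooled, 2:1 mix |
|---|---|---|
| 90% interval inside ±0.19 | 5% | about 24% |
| Non-significance at two-sided 0.05 (the plan's rule) | about 33% | 45–48% |

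With an LVAD share of 80%, the pooled figure under the plan's rule is 32–35%, no worse in practice than LVAD alone.

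**The case against.** The strongest reply has four parts.

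- *The rate is borrowed.* The 0.35 is a lung figure offered as an example, so it cannot show that LVAD power is below 80%. This stands. A reader might infer that the power claim is false for LVAD, or that no event rate could rescue it. The documents support neither: LVAD power is about 80% at a rate of 0.20, and heart-transplant power is 97% at an RVAD rate of 0.05. What can be said is that the claim is unsupported. The favourable rates do not settle the matter, because at them ±0.19 is about as large as the event rate or larger, and the plan does not justify that margin for either endpoint.
- *Pooling is not planned.* A reader might infer that a real LVAD difference will be diluted. Nothing in the plan says the endpoints will be merged. Defining them by operation and modelling each outcome points to separate analyses. Dilution also needs a smaller difference in heart patients than in LVAD patients, which is an assumption. Pooling is therefore a secondary, conditional point.
- *The rise from 5% to 24% uses a rule the plan does not have.* Correct. Under the plan's own rule the rise is smaller, and most of the risk of wrongly calling the drugs equivalent comes from that rule itself, which is a separate issue.
- *The word arm may mean lung versus heart/LVAD.* Possibly, but that group still has no common outcome, and the Table 1 footnote speaks of the primary outcomes.

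**Conclusion.** The concern holds in a limited form. The plan says it is powered for each primary endpoint, but it shows one calculation, for one lung outcome, and spends the resulting 224 on two other endpoints with no rate, margin or number of their own. The 80% is therefore unsupported for LVAD RV failure and for heart-transplant RVAD insertion.

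On separate analyses and the 2:1 volumes, LVAD power is about 57% if 0.35 applies and the drugs do not differ, and 47–51% with a true difference of 0.05. Heart-transplant power is anywhere from 49% to 97% over the assumed RVAD rates. The split, the alpha and the RVAD rates are assumptions. The gap between the claim and the calculation does not depend on them.

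**What to change.** In Table 1 and section 11:

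1. State that LVAD RV failure and heart-transplant RVAD insertion are separate primary analyses, each with its own risk difference and confidence interval. Allow an equivalence claim only for the operation whose own interval meets a margin justified for that endpoint.
2. Report any combined estimate on the 224 as secondary and stratified by operation (Mantel-Haenszel risk difference).
3. Replace the 80% with the power of each endpoint at its expected number, from a stated rate and margin for that endpoint.
4. Table 1 mentions randomisation strata without naming them. If it is not already so, make them lung transplant, heart transplant and LVAD.

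The cost is protocol and SAP wording and possibly a change to the randomisation list. No extra patients are needed, because the fix states the power honestly and does not restore 80%. At a rate of 0.35 and ±0.19, 80% for LVAD alone would take about 216 LVAD patients, or 216 × 3/2 = 324 in the joint group at a 2:1 mix. The downside is a lower stated power and no single heart/LVAD claim.
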